#### 6.3 Outcome variables and study follow-up:

6.3.1 Outcome variables

Safety outcome variables of interest (definitions provided in **Appendix**):

- Primary outcome: Major bleeding and clinically relevant non-major bleeding through 365 days of treatment with apixaban or rivaroxaban.
- Secondary outcomes:
  - To assess the frequency of major bleeding events and clinically relevant non-major bleeding individually
  - $\circ$   $\,$  To assess the frequency of intracranial and extracranial bleeding events
  - o Stroke
  - $\circ$  All-cause mortality

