	OTHER AND UNSPECIFIED INTRACRANIAL HEMORNIAGE OLEOWING INJURY WITH OPEN INTRACRANIAL WOORD WITH NO LOSS OF CONSCIOUSNESS
	OTHER AND UNSPECIFIED INTRACRAMAL HEMORRHAGE FOLLOWING INJURY WITH OPEN INTRACRAMIAL WOUND WITH MODERATE (1-24 HOURS) LOSS OF CONSCIOUSNESS
	THER AND UNSPECTED INTRACRAMIAL HEMORPHASE FOLLOWING IN JURY WITH OPEN INTRACRAMIAL WOUND WITH OPEN UNDER THAN 24 HOURS LOSS OF CONSCIOUSNESS AND RETURN TO DREEVISTING CONSCIOUS LEVEL

853.14 OTHER AND UNSPECIFIED INTRACRANIAL HEMORRHAGE FOLLOWING INJURY WITH OPEN INTRACRANIAL WOUND WITH PROLONGED( MORE THAN 24 HOURS) LOSS OF CONSCIOUSNESS AND RETURN TO PRE-EXISTING CONSCIOUS LEVEL

853.15 OTHER AND UNSPECIFIED INTRACRANIAL HEMORRHAGE FOLLOWING INJURY WITH OPEN INTRACRANIAL WOUND WITH PROLONGED (MORE THAN 24 HOURS) LOSS OF CONSCIOUSNESS WITHOUT RETURN TO PRE-EXISTING CONSCIOUS LEVEL

866.02 LACERATION OF KIDNEY WITHOUT OPEN WOUND INTO CAVITY

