363.72 HEMORRHAGIC CHOROIDAL DETACH 423 HEMOPERICARDIUM 430 SUBARACHNOID HEMORRHAGE 568.81 HEMOPERITONEUM (NONTRAUMATIC) 719.1 HEMARTHROSIS SITE UNSPECIFIED 719.13 HEMARTHROSIS INVOLVING FOREARM 719.16 HEMARTHROSIS INVOLVING LOWER LEG 719.18 HEMARTHROSIS INVOLVING OTHER SPECIFIED SITES 852 SUBARACHNOID HEMORRHAGE FOLLOWING INJURY WITHOUT MENTION OF OPEN INTRACRANIAL WOUND 852.02 SUBARACHNOID HEMORRHAGE FOLLOWING INJURY WITHOUT OPEN INTRACRANIAL WOUND WITH BRIEF (LESS THAN ONE HOUR) LOSS OF CONSCIOUSNESS 852.04 SUBARACHNOID HEMORRHAGE FOLLOWING INJURY WITHOUT OPEN INTRACRANIAL WOUND WITH PROLONGED (MORE THAN 24 HOURS) LOSS OF CONSCIOUSNESS AND RETURN TO PRE-EXISTING CONSCIOUS LEVEL 852.1 SUBARACHNOID HEMORRHAGE FOLLOWING INJURY WITH OPEN INTRACRANIAL WOUND 852.13 SUBARACHNOID HEMORRHAGE FOLLOWING INJURY WITH OPEN INTRACRANIAL WOUND WITH MODERATE (1-24 HOURS) LOSS OF CONSCIOUSNESS 852.14 SUBARACHNOID HEMORRHAGE FOLLOWING INJURY WITH OPEN INTRACRANIAL WOUND WITH PROLONGED (MORE THAN 24 HOURS) LOSS OF CONSCIOUSNESS AND RETURN TO PRE-EXISTING CONSCIOUS LEVEL 852.16 SUBARACHNOID HEMORRHAGE FOLLOWING INJURY WITH OPEN INTRACRANIAL WOUND WITH LOSS OF CONSCIOUSNESS OF UNSPECIFIED DURATION 852.2 SUBDURAL HEMORRHAGE FOLLOWING INJURY WITHOUT MENTION OF OPEN INTRACRANIAL WOUND 852.21 SUBDURAL HEMORRHAGE FOLLOWING INJURY WITHOUT OPEN INTRACRANIAL WOUND WITH NO LOSS OF CONSCIOUSNESS 852.23 SUBDURAL HEMORRHAGE FOLLOWING INJURY WITHOUT OPEN INTRACRANIAL WOUND WITH MODERATE (1-24 HOURS) LOSS OF CONSCIOUSNESS 852.24 SUBDURAL HEMORRHAGE FOLLOWING INJURY WITHOUT OPEN INTRACRANIAL WOUND WITH PROLONGED (MORE THAN 24 HOURS) LOSS OF CONSCIOUSNESS AND RETURN TO PRE-EXISTING CONSCIOUS LEVEL 852.26 SUBDURAL HEMORRHAGE FOLLOWING INJURY WITHOUT OPEN INTRACRANIAL WOUND WITH LOSS OF CONSCIOUSNESS OF UNSPECIFIED DURATION 852.29 SUBDURAL HEMORRHAGE FOLLOWING INJURY WITHOUT OPEN INTRACRANIAL WOUND WITH CONCUSSION UNSPECIFIED 852.36 SUBDURAL HEMORRHAGE FOLLOWING INJURY WITH OPEN INTRACRANIAL WOUND WITH LOSS OF CONSCIOUSNESS OF UNSPECIFIED DURATION 852.39 SUBDURAL HEMORRHAGE FOLLOWING INJURY WITH OPEN INTRACRANIAL WOUND WITH CONCUSSION UNSPECIFIED 852.4 EXTRADURAL HEMORRHAGE FOLLOWING INJURY WITHOUT MENTION OF OPEN INTRACRANIAL WOUND 852 4 EXTRADURAL HEMORRHAGE FOLLOWING INJURY WITHOUT OPEN INTRACRANIAL WOUND WITH STATE OF CONSCIOUSNESS UNSPECIFIED 852.41 EXTRADURAL HEMORRHAGE FOLLOWING INJURY WITHOUT OPEN INTRACRANIAL WOUND WITH NO LOSS OF CONSCIOUSNESS 852.44 EXTRADURAL HEMORRHAGE FOLLOWING INJURY WITHOUT OPEN INTRACRANIAL WOUND WITH PROLONGED (MORE THAN 24 HOURS) LOSS OF CONSCIOUSNESS AND RETURN TO PRE-EXISTING CONSCIOUS LEVEL EXTRADURAL HEMORRHAGE FOLLOWING INJURY WITHOUT OPEN INTRACRANIAL WOUND WITH LOSS OF CONSCIOUSNESS OF UNSPECIFIED DURATION 852.46 EXTRADURAL HEMORRHAGE FOLLOWING INJURY WITH OPEN INTRACRANIAL WOUND 852.5 852.5 EXTRADURAL HEMORRHAGE FOLLOWING INJURY WITH OPEN INTRACRANIAL WOUND WITH STATE OF CONSCIOUSNESS UNSPECIFIED 852.51 EXTRADURAL HEMORRHAGE FOLLOWING INJURY WITH OPEN INTRACRANIAL WOUND WITH NO LOSS OF CONSCIOUSNESS 852.52 EXTRADURAL HEMORRHAGE FOLLOWING INJURY WITH OPEN INTRACRANIAL WOUND WITH BRIEF (LESS THAN ONE HOUR) LOSS OF CONSCIOUSNESS EXTRADURAL HEMORRHAGE FOLLOWING INJURY WITH OPEN INTRACRANIAL WOUND WITH MODERATE (1-24 HOURS) LOSS OF CONSCIOUSNESS 852 53 852.55 EXTRADURAL HEMORRHAGE FOLLOWING INJURY WITH OPEN INTRACRANIAL WOUND WITH PROLONGED (MORE THAN 24 HOURS) LOSS OF CONSCIOUSNESS WITHOUT RETURN TO PRE-EXISTING CONSCIOUS LEVEL EXTRADURAL HEMORRHAGE FOLLOWING INJURY WITH OPEN INTRACRANIAL WOUND WITH LOSS OF CONSCIOUSNESS OF UNSPECIFIED DURATION 852.56 852.59 EXTRADURAL HEMORRHAGE FOLLOWING INJURY WITH OPEN INTRACRANIAL WOUND WITH CONCUSSION UNSPECIFIED 853 OTHER AND UNSPECIFIED INTRACRANIAL HEMORRHAGE FOLLOWING INJURY WITHOUT MENTION OF OPEN INTRACRANIAL WOUND OTHER AND UNSPECIFIED INTRACRANIAL HEMORRHAGE FOLLOWING INJURY WITHOUT OPEN INTRACRANIAL WOUND WITH BRIEF (LESS THAN ONE HOUR) LOSS OF CONSCIOUSNESS 853 02 853.06 OTHER AND UNSPECIFIED INTRACRANIAL HEMORRHAGE FOLLOWING INJURY WITHOUT OPEN INTRACRANIAL WOUND WITH LOSS OF CONSCIOUSNESS OF UNSPECIFIED 853.09 OTHER AND UNSPECIFIED INTRACRANIAL HEMORRHAGE FOLLOWING INJURY WITHOUT OPEN INTRACRANIAL WOUND WITH CONCUSSION UNSPECIFIED 853 1 OTHER AND UNSPECIFIED INTRACRANIAL HEMORRHAGE FOLLOWING INJURY WITH OPEN INTRACRANIAL WOUND WITH STATE OF CONSCIOUSNESS UNSPECIFIED 853.16 OTHER AND UNSPECIFIED INTRACRANIAL HEMORRHAGE FOLLOWING INJURY WITH OPEN INTRACRANIAL WOUND WITH LOSS OF CONSCIOUSNESS OF UNSPECIFIED DURATION 853.19 OTHER AND UNSPECIFIED INTRACRANIAL HEMORRHAGE FOLLOWING INJURY WITH OPEN INTRACRANIAL WOUND WITH CONCUSSION UNSPECIFIED 866.01 HEMATOMA OF KIDNEY WITHOUT RUPTURE OF CAPSULE WITHOUT OPEN WOUND INTO CAVITY HEMATOMA OF KIDNEY WITHOUT RUPTURE OF CAPSULE WITH OPEN WOUND INTO CAVITY 866 11 LACERATION OF KIDNEY WITH OPEN WOUND INTO CAVIT 866 12 The occurrence of Inpatient Confinement with the following attributes: Procedure Code (Any Confinement Position) is any of: { "99.05", "99.03", "99.04", "99.06" 99 05 TRANSFUSION OF PLATELETS 99.03 OTHER TRANSFUSION OF WHOLE BLOOD 99.04 TRANSFUSION OF PACKED CELLS

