#### ICD-10 Dx

- G95.19 Other vascular myelopathies
- H05.232 Hemorrhage of left orbit
- H05.239 Hemorrhage of unspecified orbit
- H31.30 Unspecified choroidal hemorrhage
- H31.301 Unspecified choroidal hemorrhage, right eye
- H31.303 Unspecified choroidal hemorrhage, bilateral
- H31.312 Expulsive choroidal hemorrhage, left eye
- H31.313 Expulsive choroidal hemorrhage, bilateral
- H31.411 Hemorrhagic choroidal detachment, right eye
- H31.419 Hemorrhagic choroidal detachment, unspecified eye
- H43.1 Vitreous hemorrhage
- H43.10 Vitreous hemorrhage, unspecified eye
- H43.11 Vitreous hemorrhage, right eye
- H43.13 Vitreous hemorrhage, bilateral
- H47.022 Hemorrhage in optic nerve sheath, left eye
- H47.023 Hemorrhage in optic nerve sheath, bilateral
- H47.029 Hemorrhage in optic nerve sheath, unspecified eye
- 160.0 Nontraumatic subarachnoid hemorrhage from carotid siphon and bifurcation
- 160.00 Nontraumatic subarachnoid hemorrhage from unspecified carotid siphon and bifurcation
- 160.01 Nontraumatic subarachnoid hemorrhage from right carotid siphon and bifurcation
- I60.1 Nontraumatic subarachnoid hemorrhage from middle cerebral artery
- I60.11 Nontraumatic subarachnoid hemorrhage from right middle cerebral artery
- 160.31 Nontraumatic subarachnoid hemorrhage from right posterior communicating artery
- I60.4 Nontraumatic subarachnoid hemorrhage from basilar artery
- 160.51 Nontraumatic subarachnoid hemorrhage from right vertebral artery
- 160.7 Nontraumatic subarachnoid hemorrhage from unspecified intracranial artery
- I60.8 Other nontraumatic subarachnoid hemorrhage
- 161.0 Nontraumatic intracerebral hemorrhage in hemisphere, subcortical
- I61.2 Nontraumatic intracerebral hemorrhage in hemisphere, unspecified
- I61.3 Nontraumatic intracerebral hemorrhage in brain stem
- I61.5 Nontraumatic intracerebral hemorrhage, intraventricular
- I61.6 Nontraumatic intracerebral hemorrhage, multiple localized
- I61.8 Other nontraumatic intracerebral hemorrhage
- I62 Other and unspecified nontraumatic intracranial hemorrhage
- I62.0 Nontraumatic subdural hemorrhage
- 162.00 Nontraumatic subdural hemorrhage, unspecified
- I62.01 Nontraumatic acute subdural hemorrhage
- 162.02 Nontraumatic subacute subdural hemorrhage
- 162.9 Nontraumatic intracranial hemorrhage, unspecified
- K66.1 Hemoperitoneum
- M25.0 Hemarthrosis
- M25.01 Hemarthrosis, shoulder
- M25.012 Hemarthrosis, left shoulder
- M25.019 Hemarthrosis, unspecified shoulder
- M25.021 Hemarthrosis, right elbow

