- M25.029 Hemarthrosis, unspecified elbow
- M25.03 Hemarthrosis, wrist
- M25.039 Hemarthrosis, unspecified wrist
- M25.05 Hemarthrosis, hip

•

ł

	Hemarthrosis, right hip
	Hemarthrosis, left hip
	Hemathrosis, knee
	Hemarthrosis, right knee
	Tematinosa, nake and foot
	Hemathrosis, right ankle
	Hemarthrosis, unspecified ankle
	Hemarthrosis, right foot
	Hemarthrosis, left foot
	Hemarthrosis, other specified site Nontraumatic hematoma of soft tissue
	Epidural hemorrhage
	Epidural hemorhage
	Epidural hemorrhage without loss of consciousness
	Epidural hemorrhage without loss of consciousness, subsequent encounter
	Epidural hemorrhage with loss of consciousness of 30 minutes or less, initial encounter
	Epidural hemorrhage with loss of consciousness of 31 minutes to 59 minutes, sequela Epidural hemorrhage with loss of consciousness of 1 hour to 5 hours 59 minutes
	Epidural hemorrhage with loss of consciousness of 1 hours to 5 hours 59 minutes, initial encounter Epidural hemorrhage with loss of consciousness of 6 hours to 24 hours
	Epidural hemorrhage with loss of consciousness of 6 hours to 24 hours
	Epidural hemorrhage with loss of consciousness of 6 hours to 24 hours, initial encounter
	Epidural hemorrhage with loss of consciousness greater than 24 hours with return to pre-existing conscious level, subsequent encounter
	Epidural hemorrhage with loss of consciousness greater than 24 hours with return to pre-existing conscious level, sequela
	Epidural hemorrhage with loss of consciousness greater than 24 hours without return to pre-existing conscious level with patient surviving, subsequent encounter
	Epidural hemorrhage with loss of consciousness of any duration with death due to brain injury prior to regaining consciousness
	Epidural hemorrhage with loss of consciousness of any duration with death due to brain injury prior to regaining consciousness, initial encounter
	Epidural hemorrhage with loss of consciousness of unspecified duration
	Epidural hemorrhage with loss of consciousness of unspecified duration, initial encounter
	Traumatic subdural hemorrhage
	Traumatic subdural hemorrhage
	Traumatic subdral hemorrhage without loss of consciousness
	Traumatic subdural hemorrhage with loss of consciousness of 31 minutes to 59 minutes
	Traumatic subdural hemorrhage with loss of consciousness of 31 minutes to 59 minutes, initial encounter
	Traumatic subdural hemorrhage with loss of consciousness of 1 hour to 5 hours 59 minutes, initial encounter

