000 01/ 3	Traumatic subarachnoid hemorrhage with loss of consciousness of 6 hours to 24 hours
	•
S06.6X4A	Traumatic subarachnoid hemorrhage with loss of consciousness of 6 hours to 24 hours, initial encounter
S06.6X4A S06.6X4S	•

- \$06.6X5S Traumatic subarachnoid hemorrhage with loss of consciousness greater than 24 hours with return to pre-existing conscious level, sequela
- S06.6X6 Traumatic subarachnoid hemorrhage with loss of consciousness greater than 24 hours without return to pre-existing conscious level with patient surviving
- S06.6X6A Traumatic subarachnoid hemorrhage with loss of consciousness greater than 24 hours without return to pre-existing conscious level with patient surviving, initial encounter
- S06.6X6S Traumatic subarachnoid hemorrhage with loss of consciousness greater than 24 hours without return to pre-existing conscious level with patient surviving, sequela
- \$06.6X7 Traumatic subarachnoid hemorrhage with loss of consciousness of any duration with death due to brain injury prior to regaining consciousness
- S06.6X8A Traumatic subarachnoid hemorrhage with loss of consciousness of any duration with death due to other cause prior to regaining consciousness, initial encounter
- S06.6X9S Traumatic subarachnoid hemorrhage with loss of consciousness of unspecified duration, sequela
- S26.0 Injury of heart with hemopericardium
- S26.01 Contusion of heart with hemopericardium
- S26.01XA Contusion of heart with hemopericardium, initial encounter
- S26.020 Mild laceration of heart with hemopericardium
- S26.020A Mild laceration of heart with hemopericardium, initial encounter
- S26.021D Moderate laceration of heart with hemopericardium, subsequent encounter
- S26.021S Moderate laceration of heart with hemopericardium, sequela
- S26.022 Major laceration of heart with hemopericardium
- S26.022D Major laceration of heart with hemopericardium, subsequent encounter
- S26.09 Other injury of heart with hemopericardium
- S26.09XD Other injury of heart with hemopericardium, subsequent encounter
- S26.09XS Other injury of heart with hemopericardium, sequela
- S37.01 Minor contusion of kidney
- S37.011D Minor contusion of right kidney, subsequent encounter
- S37.011S Minor contusion of right kidney, sequela
- S37.012A Minor contusion of left kidney, initial encounter
- S37.012D Minor contusion of left kidney, subsequent encounter
- S37.012S Minor contusion of left kidney, sequela
- S37.02 Major contusion of kidney

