H47.021	Hemorrhage in optic nerve sheath, right eye
123.0	Hemopericardium as current complication following acute myocardial infarction
131.2	Hemopericardium, not elsewhere classified
160	Nontraumatic subarachnoid hemorrhage
160.02	Nontraumatic subarachnoid hemorrhage from left carotid siphon and bifurcation
160.10	Nontraumatic subarachnoid hemorrhage from unspecified middle cerebral artery
160.12	Nontraumatic subarachnoid hemorrhage from left middle cerebral artery
160.2	Nontraumatic subarachnoid hemorrhage from anterior communicating artery
160.3	Nontraumatic subarachnoid hemorrhage from posterior communicating artery
160.30	Nontraumatic subarachnoid hemorrhage from unspecified posterior communicating artery
160.32	Nontraumatic subarachnoid hemorrhage from left posterior communicating artery
160.5	Nontraumatic subarachnoid hemorrhage from vertebral artery
160.50	Nontraumatic subarachnoid hemorrhage from unspecified vertebral artery
160.52	Nontraumatic subarachnoid hemorrhage from left vertebral artery
160.6	Nontraumatic subarachnoid hemorrhage from other intracranial arteries
160.9	Nontraumatic subarachnoid hemorrhage, unspecified
161	Nontraumatic intracerebral hemorrhage
161.1	Nontraumatic intracerebral hemorrhage in hemisphere, cortical
161.4	Nontraumatic intracerebral hemorrhage in cerebellum
161.9	Nontraumatic intracerebral hemorrhage, unspecified
162.03	Nontraumatic chronic subdural hemorrhage
162.1	Nontraumatic extradural hemorrhage
M25.00	Hemarthrosis, unspecified joint
M25.011	Hemarthrosis, right shoulder
M25.02	Hemarthrosis, elbow
M25.022	Hemarthrosis, left elbow
M25.031	Hemarthrosis, right wrist
M25.032	Hemarthrosis, left wrist
M25.04	Hemarthrosis, hand
M25.041	Hemarthrosis, right hand
M25.042	Hemarthrosis, left hand
M25.049	Hemarthrosis, unspecified hand
M25.059	Hemarthrosis, unspecified hip
M25.062	Hemarthrosis, left knee
M25.069	Hemarthrosis, unspecified knee
M25.072	Hemarthrosis, left ankle
M25.076	Hemarthrosis, unspecified foot
S06.4X0A	Epidural hemorrhage without loss of consciousness, initial encounter
S06.4X0S	Epidural hemorrhage without loss of consciousness, sequela
S06.4X1	Epidural hemorrhage with loss of consciousness of 30 minutes or less
S06.4X1D	Epidural hemorrhage with loss of consciousness of 30 minutes or less, subsequent encounter
S06.4X1S	Epidural hemorrhage with loss of consciousness of 30 minutes or less, sequela
S06.4X2	Epidural hemorrhage with loss of consciousness of 31 minutes to 59 minutes

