S06.4X5 Epidural hemorrhage with loss of consciousness greater than 24 hours with return to pre-existing conscious level S06.4X5A Epidural hemorrhage with loss of consciousness greater than 24 hours with return to pre-existing conscious level, initial encounter S06.4X6 Epidural hemorrhage with loss of consciousness greater than 24 hours without return to pre-existing conscious level with patient surviving S06 4X6A Epidural hemorrhage with loss of consciousness greater than 24 hours without return to pre-existing conscious level with patient surviving, initial encounter S06 4X6S Epidural hemorrhage with loss of consciousness greater than 24 hours without return to pre-existing conscious level with patient surviving, seguela S06.4X8 Epidural hemorrhage with loss of consciousness of any duration with death due to other causes prior to regaining consciousness S06.4X8A Epidural hemorrhage with loss of consciousness of any duration with death due to other causes prior to regaining consciousness, initial encounter S06.4X9D Epidural hemorrhage with loss of consciousness of unspecified duration, subsequent encounter S06.4X9S Epidural hemorrhage with loss of consciousness of unspecified duration, seguela S06.5X0A Traumatic subdural hemorrhage without loss of consciousness initial encounter S06.5X0D Traumatic subdural hemorrhage without loss of consciousness, subsequent encounter S06.5X0S Traumatic subdural hemorrhage without loss of consciousness, sequela S06.5X1 Traumatic subdural hemorrhage with loss of consciousness of 30 minutes or less S06.5X1A Traumatic subdural hemorrhage with loss of consciousness of 30 minutes or less, initial encounter S06.5X1D Traumatic subdural hemorrhage with loss of consciousness of 30 minutes or less, subsequent encounter S06.5X1S Traumatic subdural hemorrhage with loss of consciousness of 30 minutes or less, seguela S06.5X2D Traumatic subdural hemorrhage with loss of consciousness of 31 minutes to 59 minutes, subsequent encounter S06 5X2S Traumatic subdural hemorrhage with loss of consciousness of 31 minutes to 59 minutes, seguela S06.5X3 Traumatic subdural hemorrhage with loss of consciousness of 1 hour to 5 hours 59 minutes S06 5X4 Traumatic subdural hemorrhage with loss of consciousness of 6 hours to 24 hours S06.5X4A Traumatic subdural hemorrhage with loss of consciousness of 6 hours to 24 hours, initial encounter S06.5X4D Traumatic subdural hemorrhage with loss of consciousness of 6 hours to 24 hours, subsequent encounter S06.5X5D Traumatic subdural hemorrhage with loss of consciousness greater than 24 hours with return to pre-existing conscious level, subsequent encounter S06 5X6 Traumatic subdural hemorrhage with loss of consciousness greater than 24 hours without return to pre-existing conscious level with patient surviving S06 5X7 Traumatic subdural hemorrhage with loss of consciousness of any duration with death due to brain injury before regaining consciousness S06.5X7A Traumatic subdural hemorrhage with loss of consciousness of any duration with death due to brain injury before regaining consciousness, initial encounter S06 5X8A Traumatic subdural hemorrhage with loss of consciousness of any duration with death due to other cause before regaining consciousness, initial encounter S06 5X9 Traumatic subdural hemorrhage with loss of consciousness of unspecified duration S06.6 Traumatic subarachnoid hemorrhage S06.6X0S Traumatic subarachnoid hemorrhage without loss of consciousness, seguela S06.6X1D Traumatic subarachnoid hemorrhage with loss of consciousness of 30 minutes or less, subsequent encounter S06.6X2 Traumatic subarachnoid hemorrhage with loss of consciousness of 31 minutes to 59 minutes S06.6X2A Traumatic subarachnoid hemorrhage with loss of consciousness of 31 minutes to 59 minutes, initial encounter S06.6X2S Traumatic subarachnoid hemorrhage with loss of consciousness of 31 minutes to 59 minutes, seguela S06.6X3 Traumatic subarachnoid hemorrhage with loss of consciousness of 1 hour to 5 hours 59 minutes S06.6X3A Traumatic subarachnoid hemorrhage with loss of consciousness of 1 hour to 5 hours 59 minutes, initial encounter S06.6X3S Traumatic subarachnoid hemorrhage with loss of consciousness of 1 hour to 5 hours 59 minutes, seguela S06.6X4D Traumatic subarachnoid hemorrhage with loss of consciousness of 6 hours to 24 hours, subsequent encounter S06 6X5A Traumatic subarachnoid hemorrhage with loss of consciousness greater than 24 hours with return to pre-existing conscious level, initial encounter S06.6X5D Traumatic subarachnoid hemorrhage with loss of consciousness greater than 24 hours with return to pre-existing conscious level, subsequent encounter S06 6X6D Traumatic subarachnoid hemorrhage with loss of consciousness greater than 24 hours without return to pre-existing conscious level with patient surviving, subsequent encounter S06.6X7A Traumatic subarachnoid hemorrhage with loss of consciousness of any duration with death due to brain injury prior to regaining consciousness, initial encounter S06.6X8 Traumatic subarachnoid hemorrhage with loss of consciousness of any duration with death due to other cause prior to regaining consciousness S06 6X9 Traumatic subarachnoid hemorrhage with loss of consciousness of unspecified duration S06 6X9A Traumatic subarachnoid hemorrhage with loss of consciousness of unspecified duration, initial encounter S06 6X9D Traumatic subarachnoid hemorrhage with loss of consciousness of unspecified duration, subsequent encounter S26.00 Unspecified injury of heart with hemopericardium S26.00XA Unspecified injury of heart with hemopericardium, initial encounter S26.00XD Unspecified injury of heart with hemopericardium, subsequent encounter S26.00XS Unspecified injury of heart with hemopericardium, sequela S26.01XD Contusion of heart with hemopericardium, subsequent encounter S26.01XS Contusion of heart with hemopericardium, sequela S26.02 Laceration of heart with hemopericardium S26.020D Mild laceration of heart with hemopericardium, subsequent encounter S26.020S Mild laceration of heart with hemopericardium, sequela S26.021 Moderate laceration of heart with hemopericardium S26.021A Moderate laceration of heart with hemopericardium, initial encounter S26.022A Major laceration of heart with hemopericardium, initial encounter S26.022S Major laceration of heart with hemopericardium, sequela S26.09XA Other injury of heart with hemopericardium, initial encounter

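### Traumatic intracerebral and unspecified traumatic intracranial bleeds count as major under ICD-9 but have no code of their own under ICD-10

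*Combined protocol and SAP*

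**What the plan says.** Section 6.3.1 makes major plus clinically relevant non-major (CRNM) bleeding the primary outcome. Major bleeding on its own is a secondary outcome, and another is stated as: "To assess the frequency of intracranial and extracranial bleeding events". The codes are on the Major Bleeding and CRNM sheets of Appendix A, in separate ICD-9 and ICD-10 lists. The same sheets define the Active Bleeding exclusion over days -180 to 0.

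In the ICD-9 major list, family 853 stands in the block that comes before the transfusion condition. Examples are "853 OTHER AND UNSPECIFIED INTRACRANIAL HEMORRHAGE FOLLOWING INJURY WITHOUT MENTION OF OPEN INTRACRANIAL WOUND" and "853.15 OTHER AND UNSPECIFIED INTRACRANIAL HEMORRHAGE FOLLOWING INJURY WITH OPEN INTRACRANIAL WOUND".

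In the ICD-10 major list the corresponding block has traumatic head codes in S06.4 (epidural), S06.5 (subdural) and S06.6 (subarachnoid). The code that covers unspecified intracranial bleeding is I62.9, labelled "Nontraumatic intracranial hemorrhage, unspecified".

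**The concern.** Section 5.2.1 opens cohort entry on 28 December 2012 and closes it between the end of 2017 (CMS) and mid-2020 (Optum), so both code sets are in use. If one list takes in a type of bleed that the other leaves out, the outcome changes meaning partway through the study for reasons of coding alone.

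The bleed in question is a grave one in anticoagulated patients who fall. Falls are recorded at baseline in 2.9% of each matched arm (Appendix B). A patient with such a bleed who goes uncounted stays in follow-up as a non-event, and the major and intracranial outcomes lose serious events in the later years.

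**Working it through.** **1. The lists side by side**

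| Type of bleed | ICD-9 major, no transfusion needed | ICD-10 major, no transfusion needed | ICD-10 CRNM |
|---|---|---|---|
| Nontraumatic intracranial | 430, 431, 432 | I60, I61, I62 | none |
| Traumatic epidural, subdural, subarachnoid | 852 | S06.4, S06.5, S06.6 | none |
| Other or unspecified traumatic intracranial | 853 | none | none |

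By the lists' own labels, 853 is what remains after 852 has taken the three named sites. It therefore holds bleeding within the brain and bleeding of unspecified site. The transfusion-conditional ICD-10 block has no S06 code either.

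**2. Is the gap a product of text extraction?** The ICD-10 major list reads as two ordered runs.
- The first goes from "Nontraumatic hematoma of soft tissue" straight to epidural hemorrhage, and later from subarachnoid hemorrhage to "S26.0 Injury of heart with hemopericardium".
- The second goes from the last joint-bleed code straight to "Epidural hemorrhage without loss of consciousness, initial encounter", and later from "Traumatic subarachnoid hemorrhage with loss of consciousness of unspecified duration, subsequent encounter" to the S26.00 codes.

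Some code numbers are lost in the first run, but the labels survive. No label for traumatic cerebral, cerebellar, brainstem or unspecified intracranial bleeding appears in either run, while S06.4 to S06.6 are densely filled. The gap is in the list.

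**3. Other routes by which such a patient is still counted**
- A co-coded S06.4, S06.5 or S06.6: counted as major.
- D62 or R58 with a transfusion code: counted as major. Without transfusion: counted as CRNM.
- D64.9 or R79.1: counted as CRNM only.

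So the primary composite recovers some of these patients, though partly under the wrong component.

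**4. How many patients enter after the switch?** The documents give no switch date; October 2015 is assumed. Entry years are from Appendix B, pooled, 2016 to 2020.
- Matched rivaroxaban: 39,809 + 45,194 + 10,679 + 9,185 + 2,733 = 107,600; 107,600 / 184,107 = 58.4%.
- Matched apixaban: 39,772 + 45,182 + 10,723 + 9,103 + 2,699 = 107,479; 107,479 / 184,107 = 58.4%.
- Unmatched rivaroxaban: 40,037 + 45,661 + 10,686 + 9,185 + 2,733 = 108,302; 108,302 / 230,439 = 47.0%.
- Unmatched apixaban: 71,719 + 74,915 + 24,376 + 27,560 + 9,375 = 207,945; 207,945 / 298,310 = 69.7%.

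For these entrants all follow-up falls under ICD-10. For those who enter in early 2016, the 180-day look-back of the bleeding exclusion still reaches into ICD-9.

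**5. Effect on power for the composite.** No figure in the plan isolates these events, so the check is how far power would move. Section 10 gives Optum 68,134 matched patients and a risk of 19.8838767 per 1,000: 68,134 × 19.8838767 / 1,000 = 1,354.77 events, as stated. With 1:1 groups and two-sided alpha 0.05:

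power = Φ(√(d/4) × |ln HR| − 1.960) = Φ(18.404 × 0.2231 − 1.960) = Φ(2.147) = 0.984,

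which reproduces the stated 0.98409 at a hazard ratio of 0.8. If 1%, 5% or 10% of all primary events were lost (assumed values), Optum power would be 0.983, 0.979 or 0.974. Pooled power (15,249.77 expected events) stays at 1.00.

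**The case against.** The strongest reply is that little follows from the gap. Calendar year is balanced after matching, so both arms lose capture to about the same degree and the matched hazard ratio is little threatened. The composite takes any inpatient diagnosis position on the CRNM sheet without transfusion, and that sheet includes non-specific codes that an anticoagulated patient admitted with a head bleed may well carry. No separate intracranial code sheet is readable, so the effect on that outcome is inferred. All of this stands, and it limits the size of the point.

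Four stronger readings are tempting, and the documents do not support them:
- **Traumatic brain bleeding as a whole disappears under ICD-10.** It does not: epidural, subdural and subarachnoid bleeds after injury are still listed.
- **The gap favors one drug in the primary result.** The 58.4% in each matched arm argues against this. Only the crude row of Table 4 is unevenly exposed (47.0% against 69.7%).
- **A percentage of intracranial events is lost.** The documents give neither the number of 853-coded events nor the share of intracranial events in the composite. The 58.4% counts patients, not events.
- **Particular ICD-10 codes are the omitted equivalents.** The documents contain no crosswalk. They show only that 853 has no visible counterpart.

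The reply does not explain why the same bleed should be major by rule in one code era and unlisted in the other. It also does not restore the events that the separate major outcome loses.

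**Conclusion.** The inconsistency is real and should be corrected. Traumatic intracerebral or unspecified intracranial hemorrhage is a major bleed under ICD-9. Under ICD-10, with no other qualifying code, it drops out of the major-bleeding outcome and the primary composite, and out of the intracranial outcome if that is built from the same sheet. The Active Bleeding exclusion admits some such patients in the later era whom it would have excluded earlier.

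The consequence is an outcome definition that drifts over calendar time and under-captures major and intracranial bleeding in the period when about 58% of each matched arm enters. Material bias in the matched hazard ratio is not expected, and composite power is not at issue. The conclusion rests on an assumed US switch in October 2015 and, for the intracranial outcome, on the shared code sheet. The count of affected events is unknown from the documents.

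**What to change.** Make the ICD-9 and ICD-10 major lists equivalent and state the intent. The preferred route is to add the ICD-10 codes for traumatic cerebral, cerebellar, brainstem and unspecified intracranial hemorrhage, confirmed against the official code set. They should follow the same encounter-extension rule as the existing S06.4 to S06.6 entries, which include subsequent-encounter and sequela codes. The alternative is to remove 853 and say that this is intended.

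Apply the same change to the major outcome, the intracranial outcome and the Active Bleeding exclusion, and write down the code list for the intracranial outcome. Then check, in both arms combined, that the intracranial event rate is continuous across the switch.

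The edit is small, but changing the exclusion changes the cohort. The cohort counts, propensity-score match, balance tables and final power (Sections 5.3 and 7 to 10) must be re-run and reviewed again. Section 13 records no report name or date for a comparative run, so on the face of the document this can still be done before any treatment comparison is seen.
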